### Diagnoses

The following should be recorded on the CRFs: TB diagnosis and co-morbidities. Any other diagnosis that is, in the opinion of the site investigator, associated with study product or DHFS system, should be recorded on the adverse event CRF. The source document must include date of diagnosis and date of resolution.

### Vital Signs

Temperature, pulse, and blood pressure will be collected at all visits and kept as a part of the source document.

## 6.3.9 Laboratory Evaluations

For all visits record all Grade  $\geq$  2 laboratory values on the CRFs throughout the course of the study. All values, regardless of toxicity, of specific laboratories will also be recorded on the laboratory CRF; including: white blood cell count, neutrophil count, hemoglobin, platelets, blood urea nitrogen, creatinine, glucose, AST/ALT, alkaline phosphatase, total bilirubin.

Any laboratory toxicities that lead to a change in TB or DHFS treatment, regardless of Grade, must be recorded on the adverse event CRF.

Refer to the Division of AIDS Table for Grading Adult Adverse Experiences, which can be found on the ACTG website: <https://actgnetwork.org/>

### Hematology

Laboratory values will be done per SOC at public health and recorded in the CRF.

### Liver & Kidney Function Tests

Total bilirubin, AST (SGOT), ALT (SGPT), and alkaline phosphatase, BUN, creatinine and electrolytes (sodium, potassium, chloride, and bicarbonate) will be collated from the public health laboratory.

### Pregnancy Test

For women with reproductive potential: Urine  $\beta$ -HCG (urine test must have a sensitivity of  $\leq$  50 mIU/mL) should be done at the site's local laboratory during screening, at study entry and whenever clinically suspected.

## 6.4 Off-Drug Requirements

Additional safety monitoring and reporting of serious adverse events (SAEs) thought to be at least possibly related to DHFS will be required upon completion or discontinuation

of study protocol regardless of whether a protocol follow-up visit is scheduled to occur. Follow-up will continue until the adverse event is resolved or stabilized.

## 7.0 CLINICAL MANAGEMENT ISSUES

### 7.1 Adverse Events

Adverse events will be captured by study personnel throughout a patient’s participation in both the active portion of the protocol as well as the follow-up period. Wearable sensor-related adverse events will be captured from the onset of exposure (e.g. first patch application) to the end of device exposure (e.g. removal of last patch, or resolution of last wearable sensor-related AE, whichever is later). Ingestible sensor-related adverse events will be captured from the onset of exposure (e.g. first ingestion) to the end of device exposure (e.g. last ingestion, or resolution of last ingestible-sensor related adverse event).

Table 2. Adverse Event-Related Definitions

Adverse Event (AE)	Any undesirable medical event occurring in research subject, whether or not the event is considered related to the investigational device.
Serious Adverse Event (SAE)	An AE that results in death, is life-threatening (even if temporary in nature), results in a permanent impairment of body function or permanent damage to body structure, hospitalization, prolongation of hospitalization, or medical or surgical intervention to preclude permanent impairment of a body function or permanent damage to a body structure, or represent a serious medical event. An SAE may or may not be considered related to the investigational device.
Anticipated Adverse Event (AAE)	An AE that is listed in the clinical protocol or other study-related document that has been identified as a potential AE related to the investigational device or procedure being studied.
Unanticipated Adverse Device Effect (UADE)	Any serious adverse effect on health or safety or any life-threatening problem or death caused by, or associated with, a device, if that effect, problem or death was not previously identified in nature, severity or degree of incidence in the investigational plan or application or any other unanticipated serious problem associated with a device that relates to the rights, safety or welfare of subjects.

In some adverse event reports, the cause of the adverse event may not be immediately apparent, due to the overlapping nature of the anticipated adverse events from the DHFS and from the concomitant medications with which the patients will enroll in the study. In these cases, it is the investigator’s responsibility to appropriately adjudicate the cause of the adverse events, taking into consideration the location, nature, onset, and duration of the adverse event, as well as the

known safety profiles of both the study device, study drug, and other concomitant drugs. The following table outlines the reporting algorithm to be used for Adverse Events.

Table 3. Adverse Event Reporting Algorithm, Investigator’s (or Designee’s) Responsibilities

Type	Action	Communication
Non-Serious Adverse Event	
 
▪ Record on the CRFs
 
	Written on CRF
Serious Adverse Event (SAE), unrelated to the device	
 
▪ Record on the CRFs
 
	Written on CRF
Serious Adverse Event (SAE), possibly or definitively related to the device, anticipated	
 
▪ Record on the CRFs
 
▪ Preliminary report to Proteus Digital Health within 3 days (reporting days) of the investigator/site’s becoming aware
 
▪ Full report submitted as additional information becomes available.
 
▪ Full report submitted to the IRB within 10 working days of the investigator/site’s becoming aware
 
	Verbal and written
Unanticipated Adverse Device Effect (UADE)	
 
▪ Record on the CRFs
 
▪ Preliminary report to Proteus Digital Health within 3 days of the investigator/site’s becoming aware
 
▪ Full report to Proteus Digital Health as additional information becomes available. Report to the IRB as soon as possible, but within 10 working days of the investigator/site’s becoming aware
 
	Verbal and written

Investigators should make the required reports to the manufacturer’s Safety Officer:

[name]  
 Director of Clinical Affairs  
 Proteus Digital Health, Inc.  
 [name]  
 Phone: (Office) [contact], (Mobile) [contact], [contact]  
 Email: [contact]

Once the manufacturer has been notified of an adverse event, it will fulfill its reporting requirements to regulatory authorities per Proteus Digital Health SOP000794, *Adverse Events: Reporting Requirements for Investigational and Approved Devices*.

## 7.2 Toxicity Management

Adverse events due to Tuberculosis or the medical treatment of TB (Rifamate) will be handled per SOC and County criteria. Laboratories to monitor toxicity will be done per County criteria and will be recorded by study forms.

### Toxicity Events Related to DHFS

No adverse effects have been observed after administering the PDH ingestible sensors to rats in a dose 1,000 times the maximum human daily dose (see Investigator's Brochure). Human testing to date has included more than 250 subjects, including healthy human subjects and subjects with TB and other chronic diseases, with more than 14,000 PDH ingestible sensors ingestions. More recent studies have occurred with no exclusion for pre-existing gastrointestinal diseases. Ingestions have occurred twice daily for as long as 12 weeks, and as many as 30 PDH ingestible sensors have been ingested in a single day with no adverse gastrointestinal effect. A single occurrence of nausea and vomiting (3.5% of all subjects) has been reported after multiple earlier prototype PDH ingestible sensors ingestions in a single day. Self-limited, minor, and localized skin irritation has occurred in 17.7% wearing the adhesive backed monitor. Adhesives with improved skin tolerability are being incorporated into newer versions of the PDH system. There have been no unanticipated adverse events and no serious adverse events related, or possibly related, to the PDH System.

Skin-related issues can occur with any adhesive medical product, including the common adhesive bandage, and the wearable sensor is no exception. To date, some subjects have experienced cutaneous AEs, in the form of transient, mild, macular, papular, or maculopapular erythematous rash at the wearable sensor site. These rashes appear to be consistent with irritant (i.e., non-immune mediated) contact dermatitis, a well-characterized and common phenomenon. (It is the same phenomenon that underlies the colloquially named "dishpan hands"). Each rash in prior system studies either resolved or was resolving significantly by the time of the final safety follow-up. Experience has shown that risk of rash can be significantly mitigated by rotating wearable sensor sites with no areas of overlap.

The sponsor is committed to the rigorous capture of skin AEs related to use of the system. However, not all issues are clinically significant. Thus, the following skin-related issues shall *not* be captured as AEs by study investigators:

1. Pruritis, *if not* associated with: a) visible skin changes, including excoriation or b) interruption of system use > 1 day.
2. Skin changes that would be routinely encountered through the wear of a common adhesive bandage (e.g., transient wrinkling/whitening of the skin under a bandage, mild hyperemia).

Verification that a Skin Issue has Occurred

Before being classified as an AE, skin issues must be verified. Verification can consist of either: a) direct visualization by the investigator or his/her designee or b) a photograph taken of the affected area. The most convenient means to accomplish the latter will be use of the mobile device issued to each study subject; site staff should train each subject regarding the mobile device camera feature as he/she enters a given study. The only exception is pruritis that leads to interruption of system use > 1 day, as there likely will be nothing to visualize.

Documenting Skin AE Evolution and Chronicity

Skin AEs frequently last longer than 1 day, so a means to document the course of the AE is described below. Skin findings that occur in the same location should be treated as a single AE, unless complete resolution at that location has been visualized and documented by the investigator. Moreover, a skin AE may evolve over its course (e.g., erythema progressing to papules, followed by scaling). The investigator should therefore name the skin AE based upon findings first encountered (e.g., “macular rash”). For each assessment episode that occurs in follow-up, record the following on the *Adverse Events Form* case report form:

1. Date of assessment
2. Actions taken
3. Outcome, using the Table TBD
4. Any new features of the same skin AE that emerge on its course to resolution (e.g., scaling, non-erythematous skin discoloration) captured within the “additional skin findings” data field for a given skin AE
5. Date of onset and date of resolution

Table 4. Procedure for Documenting Device-Related Skin AE Outcome

Outcome	Definition	Action	CRF Used
Resolved	No remaining signs of skin changes	Document date of resolution	Adverse Event form used (for interim visits) OR Follow-up Visit form (for final study visit)
Resolving	Skin changes have improved but are still discernible	Document as “resolving” List any new skin findings Must continue surveillance through last study visit	Adverse Event form used (for interim visits) OR Follow-up Visit form (for final study visit)

Outcome	Definition	Action	CRF Used
Unresolved	Skin changes have not improved or have worsened	Document as “unresolved” List any new skin findings Must continue surveillance through last study visit	Adverse Event form used (for interim visits) OR Follow-up Visit form (for final study visit)
Resolved with Sequelae	Original skin issues and all subsequent skin features that were present throughout course have resolved, but a condition as a consequence of the skin AE emerged	Document as “resolved with sequelae” List the sequelae	Adverse Event form used (for interim visits) OR Follow-up Visit form (for final study visit)

On the CRF used for the last study visit (usually the safety follow-up visit), all skin AEs—except those that have not previously been documented as “resolved”—shall have a *final categorization* of outcome (“resolved,” “resolving,” “unresolved,” or “resolved with sequelae”).

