Wearable sensor version RP2 and RP3 have been cleared via the 510(k) pathway and have received the CE mark in the EU. The following is an excerpt from the FDA-cleared device label, which summarizes the safety of these earlier wearable sensor versions: “A total of 492 study subjects have participated in clinical studies representing 6,407 days of Patch (wearable sensor) use with or without ingestible sensor ingestion. Sixty-two (12.6%) of these users experienced adverse events related or possibly related to the Patch. Sixty-one of these AE were self-limited skin rashes localized to the Patch placement site, and 1 was a self-limited episode of pain at the Patch location unassociated with skin rash. None of these adverse events were considered serious.” The latest wearable sensor version (RP4), which remains investigational at present, has undergone testing in 38 subjects. Four AE were reported (10.5% of subjects), all localized to the wearable sensor placement site and mild in severity. Three of these AE were erythematous rashes at the wearable sensor location; one of these rashes transiently manifested itself as non-erythematous skin discoloration (“secondary NESD”) on the path to full resolution. The fourth AE was an episode of “primary NESD” (i.e., there was no antecedent erythematous rash reported at the wearable sensor location). Primary and secondary NESD have been encountered with previous wearable sensor versions. The investigator hypothesized that per-protocol premature removal of the wearable sensor in these studies (typically after several hours, as opposed to intended 7-day wear) significantly contributed to the occurrence of these four RP4-related AE (Wearable Sensor Investigator’s Brochure, Rev 4).

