##### Signs and Symptoms

All signs, symptoms, deaths, and toxicities must be documented in the subject's record. At entry, record all signs/symptoms experienced within 30 days of entry on the CRFs. For all other visits and at the time of occurrence of microbiologic failure, record all Grade  $\geq 2$  signs and symptoms and deaths on the CRFs that have occurred since the last visit. Any signs or symptoms that lead to a change in DHFS treatment or the investigator thinks could possibly be due to DHFS treatment, regardless of Grade, must be recorded on the CRF. The source document must include date of onset and date of resolution, but the CRF will only record prevalence of a given adverse event since the previous study visit.

Refer to the Division of AIDS Table for Grading Adult Adverse Experiences.

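### A patch-site rash that is neither seen by staff nor photographed cannot be classified as an adverse event, and no rule says how it is tabulated, so the DHFS skin event rate may be under-counted.

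*Combined protocol and SAP*

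**What the plan says.** Section 7.2, under the heading on verifying skin issues, states: "Before being classified as an AE, skin issues must be verified". Two routes are accepted: "Verification can consist of either: a) direct visualization by the investigator or his/her designee or b) a photograph taken of the affected area". For the photograph, "The most convenient means to accomplish the latter will be use of the mobile device issued to each study subject", and staff are expected to train subjects in using its camera. One event type is exempt: "The only exception is pruritis that leads to interruption of system use > 1 day, as there likely will be nothing to visualize". Section 7.2 also lists two kinds of skin finding that are not captured at all: itch without visible change or interruption beyond a day, and the ordinary changes seen under any adhesive bandage.

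Three other places describe adverse events without a verification step:

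- Section 7.1, Table 2 defines an adverse event as "Any undesirable medical event occurring in research subject, whether or not the event is considered related to the investigational device".
- Section 6.3.8, Signs and Symptoms, says that anything "the investigator thinks could possibly be due to DHFS treatment, regardless of Grade, must be recorded on the CRF". The same sentence covers signs and symptoms that lead to a change in DHFS treatment.
- Section 9.2.2, for objective 1.2.6, counts any related event of grade 1 or higher.

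On the risk itself, Section 2.2 reports 62 of 492 users of earlier patch versions with patch-related events: "Sixty-one of these AE were self-limited skin rashes localized to the Patch placement site".

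**The concern.** Section 7.2 makes verification a condition of classification. The endpoint and the general definition do not mention it. Neither Section 9.6.2 nor any other section says which governs the safety table, or where a rash goes if the subject reports it but nobody sees or photographs it.

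The gate can remove events from the count and cannot add any. It applies only to skin issues, and patch reactions arise only in subjects wearing the patch. Any loss therefore falls on the DHFS side of the objective 1.2.6 summary, which is the evidence for hypothesis 1.1.4 that DHFS is safe.

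The exemption adds an anomaly. Itch that interrupts use for more than a day counts unverified. A reported rash with the same consequence, unseen and unphotographed, is not classified as a rash event.

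Section 7.2 says that the sponsor means to capture skin events rigorously. If the reported rate depends partly on whether subjects take photographs, a low rate could not be read simply as good tolerability.

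**Working it through.** **1. Is skin reaction the main named patch risk?** The prior figures reproduce:

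- Earlier patch versions (Section 2.2): 62/492 = 12.6%, as stated. Rash share: 61/62 = 98%.
- RP4 patch (Section 2.2): 4/38 = 10.5%, as stated, all at the patch site.
- Section 7.2 separately gives 17.7% with skin irritation.

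So it is. These reactions are described as self-limited (Section 2.2) and transient (Section 7.2), so some could clear between visits.

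**2. When could a rash be seen?** Section 3.5.1 has Phase 2 subjects changing the patch themselves each week, supervised only on request. In Section 6.1, Table 1, Phase 2 adverse event evaluations fall at Day 0, Weeks 2, 4 and 8, then every 4 weeks and at end of study. The scheduled gap is 14 days up to Week 4 and 28 days after that. Phase 1 has at least five observed days a week, so the concern is mainly about Phase 2.

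**3. Chance of being present at a visit, with no photograph.** Assume a rash lasting d days that starts at a random point between visits L days apart. The probability that it overlaps a visit is d/L, capped at 1. The documents give no rash durations; 3, 5 and 7 days are assumed.

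| Assumed duration | L = 14 (to Week 4) | L = 28 (after Week 4) |
|---|---|---|
| 3 days | 3/14 = 21% | 3/28 = 11% |
| 5 days | 5/14 = 36% | 5/28 = 18% |
| 7 days | 7/14 = 50% | 7/28 = 25% |

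If the weekly County nurse visit counted as sight by a designee, L would be 7 and the figures 3/7 = 43%, 5/7 = 71% and 7/7 = 100%. The documents do not say whether that nurse is a designee.

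**4. Effect on the count.** Expected subjects with a classified skin event = 50 × prior rate × share verified. The share verified is assumed.

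| Prior rate | All verified | 75% | 50% |
|---|---|---|---|
| 10.5% | 5.3 | 3.9 | 2.6 |
| 12.6% | 6.3 | 4.7 | 3.2 |
| 17.7% | 8.9 | 6.6 | 4.4 |

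These figures carry the prior per-subject rates over to Phase 2 unchanged, although length of wear differs.

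**The case against.** The strongest reply is that the protocol already has several ways to catch such a rash:

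- Every subject has a camera-equipped study device, and photography is the intended home route. If half of subjects photographed (an assumption), a 5-day rash would be verified in 1 − 0.5 × (1 − 5/14) = 68% of cases with two-weekly visits, not 36%.
- Staff see daily patch adhesion and sensing data (Section 3.4), and an unconfirmed dose on a business day leads to contact within 24 hours (Section 3.5.1). A removed patch should prompt a call while a photograph is still possible.
- AVRC contacts intervention subjects weekly about side effects, and a County nurse sees them weekly (Section 3.5.1).
- Verification has a purpose: it separates real reactions from the ordinary bandage changes that Section 7.2 excludes.

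All of this stands as mitigation, but it does not close the gap. No text requires a photograph or says when or how to send one. Table 1 has no photograph item, and the home-use training in Section 6.2.2.1 does not mention the camera. A report by telephone does not verify a rash. Section 3.5.1 limits the County's toxicity and side-effect data in intervention subjects to non-DHFS treatment.

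A reader might infer that Section 7.2 flatly contradicts Section 6.3.8. It does not: one governs what is classified as an adverse event, the other what is recorded on the case report form, and both can be followed. An unverified rash thought to be device-related, or one leading to a change in DHFS treatment, should still reach the form. What is missing is a rule for carrying it into the adverse event count.

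A reader might also divide the 62 by the 6,407 patch-days in Section 2.2 and project events per day of wear. The 62 is a number of users (62/492 is the quoted 12.6%), so it is not an event count and does not support that projection.

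Finally, treating repeat findings as one event unless the investigator has visualized and documented resolution might look like a second source of under-counting. It applies only to the same location, Section 7.2 describes rotating sites without overlap, and it does not change the number of subjects affected.

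**Conclusion.** The point holds as a risk of under-counting, not as a demonstrated under-count. The verification rule in Section 7.2 is not reconciled with Table 2, the any-grade recording rule or the grade 1 or higher endpoint, and the plan does not say how unverified reports are tabulated. The direction is known: the rule can only lower the DHFS skin count. The size is not, because the documents give no verification rate, no rash duration and no photograph uptake.

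With half of events verified (assumed), about 5 to 9 affected subjects among 50 would appear as about 3 to 4. The visit-overlap figures are a pessimistic bound, since they assume no photograph, no prompted call and no nurse acting as designee.

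It would go too far to say that the rule decides the safety conclusion. Hypothesis 1.1.4 has no threshold or test, and objective 1.2.6 is descriptive. What is at stake is whether the reported skin rate can be interpreted.

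**What to change.** Revise Section 7.2 so that every reported patch-site skin event is entered on the adverse event form with a status field: seen / photographed / reported, not verified. Include any event that leads to patch removal or interruption, whether or not anyone saw it. Keep the two listed exclusions for findings that are not clinically significant. In the objective 1.2.6 summary, report the skin event rate for all reported events and, beside it, for verified events only. State in Section 7.2 whether a County nurse counts as a designee.

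The cost is one form field, a short rewrite of Section 7.2 and one more line in the safety table. The all-reported rate will be higher and will include some unconfirmed reports, but the verified rate stays visible next to it. The change concerns recording and reporting only; it does not alter how subjects are managed.

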### Non-Erythematous Skin Discoloration

This finding has been noted infrequently in studies of the system. Following an initially erythematous rash, the skin can take on a brownish hue in the areas of prior erythema. This should not be considered a new skin AE, as it is a continuation of the previous AE. If detected, the investigator should list “non-erythematous skin discoloration” as a new skin finding in the associated data field. On each subsequent assessment, the investigator must make the determination of “resolved,” “resolving,” “unresolved,” or “resolved with sequelae.”

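### A stray 'not' in Section 7.2 inverts the final-outcome rule for skin adverse events and sets it against Table 4

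*Combined protocol and SAP*

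**What the plan says.** The rule is in Section 7.2 (Toxicity Management), in the text that follows Table 4 under the part on documenting the evolution and chronicity of skin events. Its scope is set by "On the CRF used for the last study visit (usually the safety follow-up visit), all skin AEs". Its exception removes those "except those that have not previously been documented as" resolved. Whatever remains "shall have a *final categorization* of outcome", chosen from resolved, resolving, unresolved, or resolved with sequelae.

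Table 4 defines the same four statuses and gives an action and a form for each.
- *Resolving* means "Skin changes have improved but are still discernible".
- *Unresolved* means "Skin changes have not improved or have worsened".
- For both of these the action column says "Must continue surveillance through last study visit".
- In all four rows the form column gives the Adverse Event form for interim visits and the "Follow-up Visit form (for final study visit") as the alternative.

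The list just before Table 4 requires an outcome to be recorded at each follow-up assessment of a skin event. The next subsection, Non-Erythematous Skin Discoloration, sets a parallel rule: "On each subsequent assessment, the investigator must make the determination of" one of the same four statuses.

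**The concern.** A rule about final outcomes at a closing visit is there to settle the events that are still open. This one, as worded, does the reverse. It is a mandatory instruction in current protocol text, and staff who complete the final-visit form, or who build its entry checks, could apply it as it stands.

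Reactions at the patch site are the commonest device-related event that the protocol reports. Section 2.2 gives 62 of 492 users (12.6%) with earlier patch versions, 61 of those events being skin rashes, and 4 of 38 subjects (10.5%) with the current version. Section 7.2 gives 17.7% with skin irritation. Section 7.2 also describes earlier studies by the state of each rash at the final safety follow-up. The same statement for this trial would need the field that the literal rule lets a site leave empty. What is at stake is the completeness of a descriptive safety record that bears on hypothesis 1.1.4 and objective 1.2.6.

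**Working it through.** The protocol gives no figure to reproduce here and no arithmetic applies, so the check is one of logic. The inputs, all from Section 7.2, are the scope, exception and requirement of the sentence and the four statuses of Table 4.

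The structure is: events that need a final category = all skin events minus the excepted events.

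- As written, the excepted events are those not yet documented as resolved. What remains is the events already documented as resolved.
- With 'not' removed, the excepted events are those already documented as resolved. What remains is everything else.

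Passing each status through both forms:

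| Status recorded before the last visit | As written | With 'not' removed |
|---|---|---|
| Resolved | category required | exempt, outcome already recorded |
| Resolving | exempt | category required |
| Unresolved | exempt | category required |
| Resolved with sequelae (strict reading: never recorded as plain resolved) | exempt | category required |
| No earlier record (first seen at the last visit) | exempt | category required |

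Now compare each form with the neighbouring text.

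1. **Table 4, form column.** A final-visit form is named in the resolving and unresolved rows. That entry has a purpose only if such events receive an outcome at the final visit. The sentence as written exempts them; the sentence without 'not' requires it.
2. **The sentence's own categories.** It offers resolving and unresolved as final outcomes. As written, it reaches only events already documented as resolved, for which those two categories have next to no use. Section 7.2 also lets a finding at the same site count as a new event once the investigator has seen and documented complete resolution there, so a recurrence would ordinarily not reopen the old event.
3. **The discoloration subsection.** It asks for one of the four determinations at every later assessment and exempts nothing.

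Only the form without 'not' agrees with all three.

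**The case against.** The strongest reply is that little would be lost in practice. The list before Table 4 already asks for an outcome at each assessment, Table 4 names the form to use at the final visit, and Section 7.1 continues capture of patch-related events to removal of the last patch or resolution of the last such event, whichever is later. A sensible reader can see what was meant from the sentence's own list of categories. This stands, and it is why the point is minor. It does not remove the contradiction: two instructions in one subsection give opposite answers for the same event, and the sentence is the one that speaks expressly of the final categorisation.

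A second reply is that continued surveillance and the absence of a final category can coexist, since watching an event is not the same as classifying it. That is fair. The conflict therefore rests mainly on Table 4's form column and on the sentence's own categories, with the surveillance wording as support.

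A third reply concerns harm. A reader might infer that blank outcomes would make resolution look complete and understate persistent reactions. The documents do not support this. Nothing says that a blank is to be read as resolved. No planned analysis uses resolution status either: Section 9.2.2 defines the adverse-event endpoint as related events of grade 1 or higher, and Section 9.6.2 lists events by organ system and severity. An open event would still be counted and graded.

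**Conclusion.** The sentence is wrong as written and contradicts Table 4. It is best described as an internal inconsistency that arose in drafting, not as a design decision. The consequence is limited to a possible blank in the final-outcome field for ongoing device-related skin events at a site that applies the sentence literally. No endpoint, sample size, power or alpha depends on it.

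Two stronger statements are tempting and should not be made. The first is that every event open at the last visit would have no outcome; the other instructions still call for one, and the last interim status would usually survive. The second is a count. A reader might multiply the quoted rates by the Phase 1 enrolment: 0.105 × 75 = 7.9 and 0.177 × 100 = 17.7, or about 8 to 18. Those figures approximate subjects with any patch reaction, not events open at the last visit. To get from one to the other needs the fraction still open, which the documents do not give. Section 7.2 reports that rashes in earlier studies had resolved or were clearly resolving by final follow-up, which suggests that few remain wholly unresolved, but resolving events are also caught by the exemption. The rates come from other patch versions or from wear of a few hours, while Phase 2 intervention subjects may wear the patch for up to 12 months. The number affected cannot be derived.

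The conclusion rests on one assumption: that the rule was meant to close out open events, as Table 4 implies.

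**What to change.** Delete 'not' from the exception, so that every skin event not already documented as resolved receives a final categorisation at the last visit. In the same edit, reconcile the sentence with Table 4. State whether an event already recorded as resolved with sequelae counts as closed, and complete the unfinished table reference in the list before Table 4, which appears to mean that table. The electronic case report form is not among the documents; if its final-visit page has already been built, confirm that its outcome field follows the corrected rule.

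The cost is one word, a clarifying phrase and a check of one form. Clinical management, visits and analyses are unchanged.
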